11.5.1.2. Unexpected Adverse Event

An unexpected AE is one, the nature or severity of which is not consistent with the applicable product information that, for the present trial, is the Investigator Brochure (IB) [15].

11.5.1.3. Eliciting Adverse Event Information

The Investigator has to report all directly observed AEs and all AEs spontaneously reported by the trial patient using concise medical terminology. In addition, each trial patient will be

questioned about adverse events at each clinic visit following signature of the Informed Consent Form. The question asked will be “Since your last clinical visit have you had any health problems?”

11.5.1.4. Adverse Event Reporting Period

The adverse event reporting period for this trial begins upon signing of informed consent and ends 28 days after the last study treatment administration.

However, if a patient begins a new anticancer therapy earlier than 28 days after the last dose of study treatment administration, the adverse event reporting period will end at the time the new anticancer therapy starts.

All the adverse events that occur in trial patients during the adverse event reporting period must be reported to the Sponsor, whether or not the event is considered related to the study treatment.

11.5.1.5. Adverse Event Follow Up after the End of the Reporting Period

The following events should be followed after the end of the reporting period (i.e., 28 days after the last study treatment administration):

1. SAEs with outcome ‘not recovered’ or ‘unknown’ at the end of the reporting period.
2. Non-serious events classified as related to the investigational study treatment with outcome ‘not recovered’ or ‘unknown’ at the end of the reporting period.

These events should be followed until they resolve or until the Investigator determines, whenever possible, that they have become “chronic” or “stable”. Resolution of such events is to be documented on the SAE Form and/or on e-CRF.

In addition, if after the end of the reporting period, suspected serious adverse reactions or deaths are reported to the Investigator and he/she believes that they are related to the IMP, it is the Investigator’s responsibility to report these suspected serious adverse reactions to the Sponsor. Such suspected serious adverse reactions will be reported using a Serious Adverse Event Report or by any other way chosen by the Investigator.

11.5.1.6. Relationship to the Investigational Medicinal Product

The relationship of the adverse event will be assessed by means of the question “Is there a reasonable possibility that the event may have been caused by the study drug?” The Investigator should respond to this question with either ‘Yes’ or ‘No’.

‘No’ equals to Unrelated/Unlikely, i.e. there is no reasonable possibility that the study drug caused the event; ‘Yes’ equals to Related, i.e. there is a reasonable possibility that the study drug caused the event.

11.5.1.7. Reporting Requirements

Each adverse event has to be classified by the Investigator as SERIOUS or NON-SERIOUS (as per paragraph 11.5.1.1.2). This classification of the event determines the reporting procedures to be followed. If a serious adverse event occurs, reporting will follow local and international regulations, as appropriate.

If a serious adverse event occurs the Sponsor Pharmacovigilance has to be notified, using the designated form, within 24 hours of awareness of the event by the Investigator, by e-mail or by fax (here below Pharmacovigilance address/contacts).

e-mail: [contact]

[REDACTED]

[REDACTED]

[REDACTED]

The initial report should be followed by submission of more detailed adverse event information as soon as it is available. Additional follow-up should be provided up to the resolution of the SAE, or the Investigator determines it has become chronic or stable (not recovered) or a new anticancer therapy is initiated.

Reporting requirements for adverse events are summarized in the following table.

REPORTING REQUIREMENTS FOR ADVERSE EVENTS

Seriousness	Reporting Time	Type of Report
SERIOUS	Within 24 hours	Initial report on designated SAE form
	As soon as available	Follow-up/Final report on designated SAE form
NON-SERIOUS	As per eCRF procedure	Appropriate section of eCRF

Suspected Unexpected Serious Adverse Reactions (SUSARs) will be reported by the Sponsor to all competent Regulatory Authorities, to the Ethics Committees and to all the Investigators involved, according to local regulations and requirements stated in ICH Good Clinical Practice.

In the rare event that the Investigator does not become aware of the occurrence of a serious adverse event immediately (for example, if an outpatient trial patient initially seeks treatment elsewhere), the Investigator has to report the event within 24 hours after learning of it and document his/her first awareness of the adverse event.

Serious adverse events should also be consistently recorded in the appropriate section of e-CRF.

Non-serious adverse events have to be reported in the appropriate section of e-CRF only.

11.5.1.8. Recording Adverse Events in the Case Report Forms

Information on AEs must be evaluated by a physician and recorded in source documents such as the hospital file. AEs have to be reported in the e-CRF as aforementioned. The Investigator will also be asked to assess the relationship between the AE and the investigational medication.

- Preexisting Conditions

In this trial, a preexisting condition (i.e., a disorder present before the AE reporting period started and recorded in the pretreatment medical history form) should not be reported as AE unless the condition worsens, or episodes increase in frequency during the AE reporting period.

- Procedures

Diagnostic and therapeutic non-invasive and invasive procedures, such as surgery, should not be reported as AE. However, the medical condition for which the procedure was performed should be reported if it meets the definition of AE. For example, an acute appendicitis that begins during the AE reporting period should be reported as AE and the resulting appendectomy should be recorded in the source documents.

- Symptoms of the Disease

The specific symptoms of the disease have to be reported as adverse events if they correspond to new occurrence or to worsening of severity or frequency versus the baseline visit. Note: the general wording “Progression of the disease” should not be reported as adverse event. In case of global deterioration of health status requiring discontinuation, further data entry instructions are specified in the Study Manual.

- Abnormal Laboratory Findings

Abnormal laboratory findings have to be reported as adverse events when they cause study drug administration change (dose omission, dose delay, dose reduction, infusion interruption, drug discontinuation) or when they require clinical intervention (e.g., hospitalization for further investigation or management of the laboratory abnormality).

Note: uncomplicated and asymptomatic abnormal laboratory findings have not to be reported as adverse events. The corresponding values have to be reported only in the relevant e-CRF section (e.g., hematology, biochemistry).

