5.2.1. Definition of DLTs

For this protocol, a DLT will be defined as any of the following events for which the relationship to NMS-01940153E cannot be definitely excluded. Toxicities are to be graded according to the NCI CTCAE version 5.0 [21].

Table 1. DLT criteria	
Hematological Toxicity	
Neutropenia	Grade 4 lasting >7 days or Grade 4 of any duration associated with Grade ≥ 2 infection
Febrile neutropenia	ANC <1000/mm ³ and a single temperature of >38.3 degrees C or a sustained temperature of ≥ 38 degrees C for more than one hour.
Thrombocytopenia	Grade 3 associated with any grade bleeding or Grade 4
Anaemia	Grade ≥ 4
Non-Hematological Toxicity	
Nausea, vomiting or diarrhea	Grade ≥ 3 despite optimal treatment
Signs of potential severe drug-induced liver injury as assessed according to Hy's law	Alanine aminotransferase (ALT) or aspartate aminotransferase (AST) >3 ULN and total bilirubin >2 ULN in the absence of cholestasis (alkaline phosphatase [ALP] <2 ULN) and no other reason can be identified.
Any other non-hematological toxicities;	Grade ≥ 3 toxicities unless clear alternate etiology is documented by the investigator and except: - asymptomatic Grade 3 electrolyte changes that can be successfully supplemented (e.g., hypokalemia) and resolve/recover to baseline within 72 hours - Grade 3 fatigue that improves to \leq Grade 2 in no more than 5 days - alopecia
Other significant toxicity	
Failure to complete the first cycle of treatment with at least 66% of the planned total dose due to toxicity possibly related to the study medication	-
Failure to start Cycle 2 for more than 1 week (day 36 or later) due to persistent Grade ≥ 2 toxicities possibly related to the study medication, excluding fatigue	-
Any toxicity that is possibly related to the study medication and requires the withdrawal of the patient from the study during the DLT observation period	-
Any on-study death not clearly due to the underlying disease or extraneous causes	-

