Grade 2 despite optimal management of the event §	Omit dose; within the same cycle decrease one dose level.	Start at or maintain the decreased dose level.
Grade \geq 3 despite optimal management of the event §	Omit dose; when resolved to \leq Grade 2 within the same cycle, decrease one dose level.	Start at or maintain the decreased dose level.
Neurologic Toxicities (except insomnia/paraesthesia)		
Grade 2	Omit dose; when resolved to \leq Grade 1, decrease one dose level.	Start at or maintain the decreased dose level.
Grade $>$ 2	Consider discontinuation of study treatment based on risk/benefit assessment #.	Consider discontinuation of study treatment based on risk/benefit assessment #.
Other Non-Hematological Toxicities (except alopecia)		
Intolerable or persistent Grade 2 adverse events	Omit dose; when resolved to \leq Grade 2, maintain the dose level at first occurrence; at second occurrence, omit dose; when resolved to \leq Grade 2, decrease one dose level. .	At second occurrence, start at or maintain the decreased dose level.

Table 6. Dose Reductions/Treatment Discontinuations for NMS-01940153E Based on the Worst Grade (as per NCI CTCAE Criteria, Version 5.0) Observed During a Treatment Cycle and in the Prior Treatment Cycle

Toxicity	Dose Adjustment during treatment cycle	Next cycle Starting Dose
Grade 3	Omit dose; when resolved to \leq Grade 2, decrease one dose level.	Start at or maintain the decreased dose level.
Grade 4	Omit dose; when resolved to \leq Grade 2, decrease one dose level or consider study treatment discontinuation [#]	Start at or maintain the decreased dose level or consider study treatment discontinuation [#]
Grade \geq 3 hypersensitivity reaction suggestive of anaphylactic reaction [#]	Study treatment discontinuation	Study treatment discontinuation.

§ For prophylaxis and management of the events, see details in Supportive Care Sections 9.2.7.
 ‡ lasting longer than 48h without resolution to grade 2 or better and judged at least possibly related to NMS-01940153E.

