11.5.1. Adverse Event Assessment

11.5.1.1. Definition of Adverse Events

11.5.1.1.1. Adverse Event

According to ICH definition and EU Regulation (No. 536/2014), an AE is defined as any untoward medical occurrence in a subject to whom a medicinal product is administered and which does not necessarily have a causal relationship with this treatment. An adverse event can therefore be any unfavorable and unintended sign (e.g., an abnormal laboratory finding), symptom, or diagnosis temporally associated with the use of a medicinal product, whether or not considered related to the medicinal product.

Any untoward medical occurrence, which occurs outside the period of patient follow-up defined in the protocol, is not considered an AE. Symptoms or medically significant laboratory or instrumental (e.g., by electrocardiography) abnormalities of a pre-existing condition should not be considered an AE. However, occurrence of new symptoms, laboratory or instrumental abnormalities, as well as worsening of pre-existing ones, is considered AEs.

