- *Blood chemistry* (local laboratory) includes: glucose, electrolytes (Na, K, Ca, P, magnesium), urea or BUN (Phase II), serum creatinine, creatinine clearance (calculated with Cockcroft-Gault equation), total protein, albumin, aspartate aminotransferase (AST/SGOT), alanine aminotransferase (ALT/SGPT), gamma-GT, total bilirubin, unconjugated bilirubin, alkaline phosphatase (ALP), lactate dehydrogenase (LDH). The assessment is mandatory, at screening (≤ 7 days from treatment start). During treatment on Phase I, blood chemistry should be done from cycle 1 to cycle 3, on days 1, 8, 15, 22 and, from cycle 4 onward, on days 1, 8, 15; during treatment on Phase II, blood chemistry should be done on cycle 1, on days 1, 8, 15, 22 and, from cycle 2 onward, on days 1, 15. In case of cycle delay due to toxicity and/or if clinically indicated, additional assessments should be done as per medical judgment; blood chemistry should be repeated at the start of the delayed cycle. All blood chemistry assessments performed during the treatment period can be done the day before the scheduled one; on days of treatment administration, sampling should be performed, and results should be available before the start of NMS-01940153E infusion. Blood chemistry should be performed also at EoT and 28-days follow up visits. Note: at Cycle 1 Day 1, blood chemistry does not need to be repeated before study drug administration if it was performed at screening within 24 hours from treatment start.

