9.8.2. Dose Limiting Toxicities

A DLT will be defined as any of the adverse events described in MPSA-153-001 Clinical Protocol Section 5.2.1 occurring in Cycle 1, during Phase I dose escalation, for which the relationship to NMS-01940153E cannot be definitely excluded. Toxicities are to be graded according to the NCI CTCAE version 5.0 [13]. In particular:

Hematological Toxicity

- Neutropenia Grade 4 lasting >7 days or Grade 4 of any duration associated with Grade ≥ 2 infection
- Febrile neutropenia ANC <1000/mm³ and a single temperature of >38.3 degrees C or a sustained temperature of ≥ 38 degrees C for more than one hour.
- Thrombocytopenia Grade 3 associated with any grade bleeding or Grade 4
- Anaemia Grade ≥ 4

Non-Hematological Toxicity

- Nausea, vomiting or diarrhea Grade ≥ 3 despite optimal treatment
- Signs of potential severe drug-induced liver injury as assessed according to Hy's law: Alanine aminotransferase (ALT) or aspartate aminotransferase (AST) >3 ULN and total bilirubin >2 ULN in the absence of cholestasis (alkaline phosphatase [ALP] <2 ULN) and no other reason can be identified.
- Any other non-hematological toxicities: Grade ≥ 3 toxicities unless clear alternate etiology is documented by the investigator and except:
 - asymptomatic Grade 3 electrolyte changes that can be successfully supplemented (e.g., hypokalemia) and resolve/recover to baseline within 72 hours
 - Grade 3 fatigue that improves to \leq Grade 2 in no more than 5 days
 - alopecia

Other significant toxicity

- Failure to complete the first cycle of treatment with at least 66% of the planned total dose due to toxicity possibly related to the study medication
- Failure to start Cycle 2 for more than 1 week (day 36 or later) due to persistent Grade ≥ 2 toxicities possibly related to the study medication, excluding fatigue
- Any toxicity that is possibly related to the study medication and requires the withdrawal of the patient from the study during the DLT observation period

Statistical Analysis Plan

- Any on-study death not clearly due to underlying disease or extraneous causes

For the Phase I part only, first cycle DLT analysis will be performed on the dose-limiting toxicity evaluable set. For each dose level, patients who experienced a DLT during the first cycle of treatment and type of DLT experienced, will be reported in a data listing.

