9.8.4. Clinical Laboratory Evaluations

Quantitative laboratory variables (hematology, blood chemistry, coagulation) will be summarized using mean, standard deviation, minimum, maximum and median, by study phase and dose level at each visit. At each cycle, the same descriptive statistics of within-subject changes from baseline measurements will be also presented.

The following laboratory data will be graded from Grade 1 up to Grade 4 according to the NCI CTCAE scale (version 5.0): hemoglobin (except Grade 4 for anemia), platelets, white blood cells (except Grade 4 for leukocytosis), neutrophils, lymphocytes, glucose (graded only for glucose decrease; i.e. hypoglycemia), sodium (graded only for sodium increase; i.e. hypernatremia), potassium (graded only for potassium increase; i.e. hyperkalemia), total calcium after correction with albumin, magnesium, creatinine, albumin (except Grade 4), aspartate aminotransferase (AST), alanine aminotransferase (ALT), alkaline phosphatase (ALP), gamma-GT (GGT), total bilirubin and lactate dehydrogenase (LDH) (only Grade 1 possible). For lab tests reported in the NCI CTCAE scale for which the grading system is based mainly on clinical assessments, the grade will not be calculated. For example, this applies to eosinophils, glucose (hyperglycemia), phosphorus (both hyperphosphatemia and hyperphosphatemia), sodium (hyponatremia), potassium (hypokalemia) and INR.

Laboratory abnormalities will be summarized in frequency distribution tables by study phase, dose level and treatment period (i.e. treatment Cycle 1, Cycle >1 and the whole treatment period).

For each parameter graded according to NCI CTCAE scale, patients will be classified based on the maximal severity grade observed during the analyzed time-window. Changes of severity grade

Statistical Analysis Plan

vs. baseline will be evaluated by shift tables. Selected laboratory parameters will be further explored by analyzing the nadir/zenith values, the time to nadir/zenith and the time to recovery after nadir/zenith, as clinically appropriate.

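### The combined liver-injury pattern counts only as a Phase I Cycle 1 DLT: beyond that no passage names it as an AE or notification trigger, and the SAP text has no combined summary

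*Protocol*

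**What the plan says.** **DLT definition.** Protocol 5.2.1, Table 1, has a separate row: "Signs of potential severe drug-induced liver injury as assessed according to Hy's law". It requires ALT or AST >3 ULN, total bilirubin >2 ULN, ALP <2 ULN and no other identified reason. SAP 9.8.2 repeats it, restricted to Cycle 1 of dose escalation: "For the Phase I part only, first cycle DLT analysis will be performed on the dose-limiting toxicity evaluable set". Under protocol 5.2.2 the window closes at the first Cycle 2 dose.

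**Dosing.** Table 6 has no hepatic or combined row. Liver tests fall under its catch-all for other non-hematological toxicities, which acts on Grade 3, Grade 4, or "Intolerable or persistent Grade 2 adverse events". Section 9.2.3.2 lets a new cycle start only when toxicities are Grade ≤1 or back to baseline.

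**AE recording.** Under 11.5.1.8 a laboratory finding must be reported as an AE if it changes dosing or needs clinical intervention. A note adds that "uncomplicated and asymptomatic abnormal laboratory findings have not to be reported as adverse events"; such values go only to the laboratory pages of the eCRF. Section 11.5.1.1.1 says instead that "occurrence of new symptoms, laboratory or instrumental abnormalities, as well as worsening of pre-existing ones, is considered AEs". Under 11.5.1.7, seriousness is classified, and 24-hour notification decided, for adverse events.

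**Schedule and analysis.** Phase II chemistry is drawn on days 1, 8, 15 and 22 of Cycle 1, then "from cycle 2 onward, on days 1, 15" (11.5.2). SAP 9.8.4 states: "For each parameter graded according to NCI CTCAE scale, patients will be classified based on the maximal severity grade observed".

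**The concern.** The protocol cites compromised liver as a reason for caution in this population, and its own Table 1 treats the combination as a sign of possible severe drug injury. With no comparator arm, transaminases and bilirubin rising together is one of the few signals that can separate drug injury from background enzyme elevation. Entry allows ALT/AST up to 5 × ULN, so the transaminase part of the pattern can be present at baseline. Bilirubin is capped at 1.5 × ULN at entry (Gilbert's syndrome excepted), so a rise above 2 × ULN is new information.

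Outside the DLT assessment, nothing requires this combination to be flagged, assessed for seriousness or notified. The Phase II hold rule in 12.4 counts Grade 4 adverse events, so a low-grade case does not enter it. Sites also face two conflicting instructions on whether an asymptomatic laboratory abnormality is an AE, and may record the same values differently.

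**Working it through.** The plan gives no figure on this point, so there is none to reproduce. The check follows the pattern through the documents.

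**1. Where it is used.** It appears in the protocol synopsis, Table 1 and SAP 9.8.2, each time as a DLT criterion. It does not appear in Table 6, 11.5.1.7, 11.5.1.8, 12.4 or SAP 9.8.4.

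**2. Why low-grade cases matter.** Table 1 has another row for any other non-hematological toxicity of Grade ≥3. A separate liver row adds something mainly when neither component reaches Grade 3.

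**3. Which cases can go unrecorded.** The documents cite CTCAE v5.0 but do not print its cut-offs. Assumed cut-offs for Grades 1/2/3/4: ALT >1, >3, >5, >20 × ULN with a normal baseline, or >1.5, >3, >5, >20 × baseline if abnormal; bilirubin >1, >1.5, >3, >10 × ULN, or × baseline if abnormal. The last column shows the range by grading every value against ULN. All rows assume ALP <2 × ULN and no other cause.

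| Baseline ALT / bilirubin (× ULN) | On treatment (× ULN) | Grades, baseline-relative | Grades, ULN only |
|---|---|---|---|
| 1 / 1 | 3.5 / 2.2 | 2 / 2 | 2 / 2 |
| 1 / 1 | 6 / 2.2 | 3 / 2 | 3 / 2 |
| 4 / 1.5 | 4.5 / 2.1 | 0 / 1 (4.5/4 = 1.13; 2.1/1.5 = 1.4) | 2 / 2 |
| 5 / 1.5 | 7 / 2.2 | 0 / 1 (7/5 = 1.4; 2.2/1.5 = 1.47) | 3 / 2 |

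Every row meets ALT >3 and bilirubin >2. The 1.5 × ULN baselines are eligible if they do not exceed 2 mg/dL, that is, if ULN ≤ 2/1.5 = 1.33 mg/dL.

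- A Grade 3 component calls for dose omission under Table 6, which makes the finding an AE.
- With both components at Grade 2, Table 6 acts only if the event is intolerable or persistent. Its release condition, resolution to Grade ≤2, is already met by a Grade 2 event. If the values have not recovered by the next day 1, 9.2.3.2 delays the cycle and the finding becomes an AE. If they have recovered, it need not be recorded.
- At Grades 0 and 1 there is no Table 6 action and no delay, so 11.5.1.8 requires no AE even if the values persist.

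**4. What the summaries show.** Separate maximum grades cannot establish concurrence. A patient with Grade 2 ALT in Cycle 1 and Grade 2 bilirubin in Cycle 3 has the same whole-treatment maxima as one with both at a single visit.

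**5. Scale.** Phase II may enrol up to 40 patients, against 12–15 expected in Phase I. No rate for the pattern is given. If a patient's chance of showing it were 1%, 2% or 5% (assumed), the chance of at least one case among 40 is 1 − (1 − p)^40 = 0.331, 0.554 or 0.871. Unflagged cases are some unknown part of these.

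**The case against.** The strongest reply is that the DLT label exists to find the MTD, so its ending with the window is by design. Table 6 and section 11.5 are not phase-specific; Phase I also had no liver dosing row and no expedited trigger. Any Grade 3–4 component, or an unresolved Grade 2 at cycle start, changes dosing and becomes an AE. An investigator may decide that such a pattern is not uncomplicated, or report it as an important medical event. Section 11.5.2 also makes a clinically significant, drug-related value still abnormal after the 28-day follow-up an AE. All of this stands, and it narrows the gap, but discretion is not a stated trigger.

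Three stronger readings are tempting and are not supported:

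- A reader might infer that the pattern drops out only in Phase II. It is equally unnamed in Phase I after Cycle 1.
- A reader might take a case on day 15 of Cycle 2 as a DLT had it occurred in Phase I. The window has closed by then. Day 15 is also the last infusion of the cycle, so the 14 days to the next day 1 contain no further dose.
- A reader might conclude that the sponsor and DSMB would miss such a case altogether. The values are entered in the eCRF, listed for every treated patient and summarised analyte by analyte, and the DSMB's remit covers safety data beyond AEs and SAEs.

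On the chemistry schedule, Table 4, its footnote and 11.5.2 all agree on days 1 and 15 from cycle 2. The requirement for results before infusion can be read as covering scheduled samples only. This is a wording question and does not carry the point.

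**Conclusion.** The point holds in a limited form. Outside the Phase I Cycle 1 DLT assessment, no passage makes the protocol's own liver-injury pattern an AE or an expedited-report trigger, and the SAP text describes no summary of the combination. An uncomplicated, asymptomatic case with no Grade 3–4 component, no dosing change and no intervention need not be recorded as an AE under 11.5.1.8, while 11.5.1.1.1 would make it one. The loss is the AE flag, the seriousness assessment and prompt notification; the data themselves are kept.

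The missing trigger, the missing combined summary and the conflict between sections rest on the text alone. The worked cases rest on the assumed CTCAE cut-offs, and the Grade 0/1 cases also on baseline-relative grading. The separate appendix of table mock-ups and algorithms was not available, so a combined table there cannot be excluded. The number of affected patients cannot be estimated from the documents. This should be corrected, but it does not undermine the design.

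**What to change.** (a) Align 11.5.1.1.1 with 11.5.1.8. State in 11.5.1.8 and 11.5.1.7 that any on-treatment laboratory set meeting Table 1's own liver definition is recorded as an AE and notified promptly to the sponsor, whether or not it is symptomatic or changes dosing.

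(b) In SAP 9.8.4, add one table and one listing of patients with concurrent ALT or AST >3 ULN and bilirubin >2 ULN with ALP <2 ULN, showing baseline values. If the separate appendix already holds such a table, refer to it in the SAP text.

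(c) The sponsor should also reconcile Table 6 with Table 1 for this pattern, and the day 1 and 15 chemistry schedule from cycle 2 with the wording on results before infusion on treatment days. No dosing or clinical rule is proposed.

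For (a) and (b) the cost is protocol wording, one programmed table and listing, and a few extra reports. Some will be false positives in patients with raised baseline transaminases or biliary progression; showing baseline values helps to identify the former. All four analytes are already collected, so no new assay is needed.
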